This material is the property of the University of Pennsylvania. Do not disclose or use except as authorized in writing by the study sponsor.

The primary objectives of the trial include determination of ORR per RECIST 1.1 for the combination of pembrolizumab and itacitinib and the safety of this combination, as assessed by CTCAE. Pre-specified adverse events of clinical interest include the following events: 1) Grade  $\geq$  3 diarrhea 2) Grade  $\geq$  2 colitis, 3) Grade  $\geq$  2 pneumonitis, 4) Grade  $\geq$  3 hypo- or hyperthyroidism, 5) Grade  $\geq$  2 hypophysitis, 6) Grade  $\geq$  2 uveitis, 7) Grade  $\geq$  2 nephritis, 8) Grade  $\geq$  3 anemia, 9) Grade  $\geq$  3 thrombocytopenia, and 10) Grade  $\geq$  3 neutropenia.

The secondary objective of this trial is to collect paired tumor biopsies and peripheral blood to characterize immune biomarkers of response to treatment with pembrolizumab and itacitinib. Additional secondary objectives include determination of progression free survival, duration of response and overall survival, up to week 16 when the subject reaches end of study.

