## 6.0 TRIAL FLOW CHART

### 6.1 Study Flow Chart

Trial Period:	Treatment Cycles (q3 weeks)					End of Study Treatment 	End of Study 
Treatment Cycle/Title:	Screening Visit	Cycle1	Cycle 2	Cycle 3	Cycle 4	EOT Safety Follow-up Visit	
Scheduling Window (Days):	-28 to -1	Wk1	Wk 3 (± 3)	Wk 6 (± 3)	Wk 9 (± 3)	Week 12 (±5)	Week 16(±10)
Informed Consent	X						
Inclusion/Exclusion Criteria Assessment	X						
Demographics and Medical History	X						
Prior and Concomitant Medication Review	X	X-----X				X	
Pembrolizumab Administration		X	X	X	X		
Itacitinib Administration				X	X		
Post-study anticancer therapy status						X	X
Adverse Event Assessment	X	X-----X				X	X
Full Physical Examination	X				X	X	
Directed Physical Examination 		X	X	X			X
Vital Signs and Weight	X	X	X	X	X	X	
ECOG Performance Status	X	X	X	X	X	X	
Pregnancy Test – Urine or Serum β-HCG 	X	X 					
PT/INR and aPTT	X 						
CBC with Differential 	X 		X	X	X	X	X
Comprehensive Serum Chemistry Panel 	X 		X	X	X	X	X

CONFIDENTIAL

This material is the property of the University of Pennsylvania. Do not disclose or use except as authorized in writing by the study sponsor.

Trial Period:	Treatment Cycles (q3 weeks)					End of Study Treatment 	End of Study 
	Screening Visit	Cycle 1	Cycle 2	Cycle 3	Cycle 4		
Treatment Cycle/Title:	-28 to -1	Wk1	Wk 3 (± 3)	Wk 6 (± 3)	Wk 9 (± 3)	Week 12 (±5)	Week 16(±10)
TSH 	X 		X			X	
Tumor Imaging 	X 		X 		X 		
Tumor Biopsies 			X 		X 		
Archived Tumor Tissue Sample Collection	X 						
Research Blood Collection 	X	X	X	X	X	X	

1. The order of preference for biopsy site, if safely accessible, is primary tumor > solid organ metastasis (including thoracentesis) > lymph node metastasis. Preference will be made to biopsy the same site for both biopsies, if safe and feasible.
2. Up to 78mL of blood will be collected for research studies. Please refer to the Study Laboratory Manual for additional details related to sample collection and handling.
3. Female subjects of reproductive potential only. A negative pregnancy test is required within 72 hours of Cycle 1/Day 1.
4. Directed physical examinations will be symptom and disease driven based on physician discretion.

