### **7.1.2.3 *Directed Physical Exam***

For cycles that do not require a full physical exam per the Trial Flow Chart, the investigator or qualified designee will perform a directed physical exam as clinically indicated prior to trial treatment administration. Directed physical examinations will be symptoms and disease driven based on physician discretion.

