### **8.2.3 Statistical Methods**

#### Primary Objectives

1. Based on evaluable subjects, the objective response rate and 95% confidence interval will be calculated.
2. Toxicities will be graded, categorized and tabled. Toxicity tables will be separately constructed for cycles with pembrolizumab alone (cycles 1-2 and cycle  $\geq 5$ ) or pembrolizumab and itacitinib (cycles 3-4).

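### No TSH is scheduled between Cycle 2 and Week 12, so a thyroid laboratory change that begins before itacitinib can be tabled under the combination

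*Combined protocol and SAP*

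**What the plan says.** - Section 8.2.1 names two primary endpoints, response rate and tolerability. Tolerability is judged from CTCAE reporting.
- Section 8.2.3 (Primary Objectives) gives the only stated tolerability analysis: "Toxicity tables will be separately constructed for cycles with pembrolizumab alone", meaning cycles 1-2 and 5 onward, and for the two drugs together, meaning cycles 3-4. Section 8.2 repeats this and puts every toxicity seen into the tables, so low grades count. Neither section says whether onset date or detection date places an event in a cycle.
- The Section 6.1 flow chart marks TSH at screening, Cycle 2 (week 3) and Week 12. Cycle 3, Cycle 4 and Week 16 are blank.
- The blood count row of the same chart reads "CBC with Differential 8 X 9 X X X X X" (8 and 9 are footnote marks): screening, Cycles 2, 3 and 4, Week 12 and Week 16. The chemistry row is identical.
- Footnote 8 treats cycle laboratory tests after Cycle 1 as pre-dose, up to 72 hours ahead. Section 5.3.2 starts itacitinib on Cycle 3 Day 1.
- Section 10.1 allows a laboratory abnormality to be an adverse event in its own right, and Section 10.2 asks for its start date.
- Section 2.1 lists Grade ≥ "3 hypo- or hyperthyroidism" among the events of clinical interest.

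**The concern.** Each cycle's draw precedes that cycle's dose, so it reflects the cycle just completed. The Cycle 2 TSH therefore closes cycle 1, and no TSH closes cycle 2. The next value, at Week 12, covers cycle 2 on pembrolizumab alone together with both itacitinib cycles. A thyroid change without symptoms that starts in weeks 3-6 will normally be dated to the sample that shows it, and that sample falls in the cycles 3-4 table.

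A change arising in a fifth cycle has no scheduled TSH to find it, although that cycle belongs to the pembrolizumab-alone table. Both gaps act in the same direction: they remove thyroid findings from the pembrolizumab-alone column, and the first adds them to the combination column.

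The trial has one arm, so a reader will look to the two sets of tables for what itacitinib appears to add. For thyroid laboratory findings, part of any difference would come from when blood was tested.

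**Working it through.** The plan states no figure on this point, so there is none to reproduce. The check is a reading of the schedule followed by simple arithmetic.

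**Step 1: the row.** The chart has seven visit columns. As an alignment check, the imaging marks carrying footnotes 10 (after Cycle 2) and 11 (end of Cycle 4) fall in the Cycle 2 and Cycle 4 columns. The TSH mark after screening is in that same Cycle 2 column.

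**Step 2: which draw closes each cycle (nominal days).**

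| Cycle | Days | CBC and chemistry | TSH |
|---|---|---|---|
| 1, pembrolizumab alone | 0-21 | Cycle 2 pre-dose | Cycle 2 pre-dose |
| 2, pembrolizumab alone | 21-42 | Cycle 3 pre-dose | none until Week 12 |
| 3, combination | 42-63 | Cycle 4 pre-dose | none until Week 12 |
| 4, combination | 63-84 | Week 12 | Week 12 |
| 5, optional, pembrolizumab alone | after 84 | Week 16 | none |

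The Week 12 TSH covers 84 − 21 = 63 days, of which 42 − 21 = 21 (33%) precede itacitinib.

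**Step 3: share by table.** Assumptions, none of them in the documents: constant onset hazard over weeks 0-12, no itacitinib effect, detection only by the first scheduled TSH after onset, and assignment by detection date. For a rare event, the share recorded under pembrolizumab alone is 21/84 = 25%. The share that begins there is 42/84 = 50%.

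**Step 4: size in subjects.** Let F be the 12-week cumulative incidence. The daily hazard is −ln(1 − F)/84, so the probability of onset by day t is 1 − (1 − F)^(t/84). Use t = 21 for recorded and t = 42 for true.

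| Assumed F | Recorded, alone | True, alone | Difference | Of 48 subjects |
|---|---|---|---|---|
| 5% | 1.3% | 2.5% | 1.3 points | 0.6 |
| 10% | 2.6% | 5.1% | 2.5 points | 1.2 |
| 20% | 5.4% | 10.6% | 5.1 points | 2.5 |

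(Differences are taken before rounding.) At F = 10% the combination column shows 10 − 2.6 = 7.4%, against a true 10 − 5.1 = 4.9%.

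**Step 5: sensitivity.** The Cycle 2 draw can fall on days 15-24 (day 21 ± 3, less up to 72 hours) and the Week 12 draw on days 79-89. The recorded share then runs from 15/89 = 17% to 24/79 = 30%. At nominal days, hazards of 0.001 to 0.05 per week give 25% to 31%.

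**Step 6: with a Cycle 3 pre-dose TSH.** The share recorded under pembrolizumab alone becomes 42/84 = 50%, the same as CBC and chemistry already have.

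**The case against.** The strongest reply is that little depends on this. The tables are descriptive, and no test or ratio between periods is planned. Section 10.2 requires adverse event questioning at every contact, and Section 7.1 allows unscheduled tests, so symptomatic thyroid disease would be found when it occurs. The thyroid event of clinical interest is Grade 3 or higher, which depends least on a scheduled TSH. Assignment by detection date is an assumption. Pembrolizumab alone also always comes first for cycles 1-2, so time and cumulative exposure stay confounded with itacitinib whatever is measured.

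Most of this stands, and it limits the point to silent, mainly low-grade laboratory findings. None of it supplies a scheduled TSH at the switch. The missing assignment rule is part of the gap, because without a Cycle 3 value an onset-based rule could not be applied to a silent change either. The confounding by time is a reason to read the tables cautiously, but it does not excuse an avoidable misallocation.

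A reader might go further and infer that TSH is measured more heavily in cycles 3-4, or not at all before itacitinib. The flow chart supports neither: after baseline there is one draw on each side, counting Week 12 with the combination, and two draws (screening and Cycle 2) precede itacitinib.

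A reader might also point to the examinations. Full ones fall at screening, Cycle 4 and Week 12, while at Cycles 1-3 and Week 16 "Directed physical examinations will be symptom and disease driven based on physician discretion". That difference is real, but every treatment visit has an examination of one kind or the other. The documents give no basis for sizing any effect on recorded toxicity, so no change is asked for there.

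**Conclusion.** The point holds for thyroid laboratory findings. On the schedule as written, about 25% of laboratory-only thyroid events in weeks 0-12 (17-30% across visit windows) would be recorded under pembrolizumab alone although about 50% begin there. At an assumed 10% incidence this moves about 1 of 48 subjects from one table to the other; the range is 0.6 to 2.5 subjects for 5% to 20%. These figures rest on constant hazard, laboratory-only detection and assignment by detection date. Symptomatic detection makes them smaller.

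It would be wrong to infer that the schedule makes toxicity as a whole look higher on the combination. CBC and chemistry are drawn at every switch point, and adverse event questioning is the same throughout. The Bayesian toxicity rule in Section 5.9 counts subjects cumulatively without splitting by cycle, so it is unaffected. This is a small, directional fault in one part of a primary endpoint's presentation. It is worth correcting because the remedy is so cheap.

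**What to change.** 1. In the Section 6.1 flow chart, add TSH to the Cycle 3 pre-dose draw, before the first itacitinib dose.
2. Add TSH to the Week 16 draw when a fifth cycle was given.
3. In Section 8.2.3, add one sentence: for subjects with no Cycle 3 TSH, thyroid laboratory abnormalities first found at Week 12 are tabled as onset weeks 3-12, period not determinable, and not under cycles 3-4. This also serves subjects already treated.

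The cost is one or two extra assays per subject on blood already being drawn, a flow chart edit and one SAP sentence. No added visit or venepuncture is needed.

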#### Secondary Objectives

1. Changes in immune pharmacodynamic biomarkers will be examined with scatter plots and summary statistics. Fold changes from baseline values will be estimated and summarized.
2. Duration of response, progression-free survival and overall survival will be estimated by the method of Kaplan and Meier. Median values and 95% confidence intervals will be calculated.

CONFIDENTIAL

This material is the property of the University of Pennsylvania. Do not disclose or use except as authorized in writing by the study sponsor.

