### **3.2 Secondary Objectives**

- 1) To collect paired blood and tumor tissue samples in order to perform mechanistic studies on treatment-related changes in the subject and tumor immune profiles
- 2) To determine the median progression free survival (PFS) and duration of response (DOR) at week 12 as well as overall survival (OS) for subjects treated with pembrolizumab and itacitinib, up week 16.

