##### **4.2.3.1.2 Secondary**

Peripheral blood immune profiling will provide important mechanistic information on how PD-1 blockade and itacitinib function in human subjects. By studying treatment related changes in blood and tumor, and correlate these with response or resistance, superior and perhaps tailored combination treatment strategies could potentially be developed in the future. Correlative samples will be banked upon receipt and correlative assays performed in the following priority order.

High priority assays:

1. Multiparametric flow cytometry analysis of peripheral blood mononuclear cells to analyze T cell subsets and markers of functionality. T cell subsets will be determined using transcription factors and surface markers subsets. Functionality will be measured by examining activation markers, cytokines, effector molecules, and proliferation markers.
2. Transcriptomic analyses of tumor specimens to identify changes in gene expression after the addition of itacitinib to pembrolizumab. In particular, we will examine a subset of interferon-stimulated genes (ISGs) associated with resistance to checkpoint blockade in pre-clinical models.
3. Measurement of inflammatory cytokine or chemokine levels in subject serum. In particular, we will examine interferon levels and other cytokines regulated by the JAK1 pathway as biomarkers for both on-target drug activity and response.

Second priority assays:

1. Measurement of inflammatory cytokine or chemokine levels in subject serum. Circulating tumor cell (CTC) and circulating tumor DNA (ctDNA) measurements and profiling.

Additional secondary endpoints include progression free survival (PFS), overall survival (OS) and duration of response (DOR). PFS is defined as days from initiation of study therapy to first documented disease progression, death due to any cause or last subject contact which documents progression-free status. Those patients who are currently on-study and progression-free at 16 weeks, will no longer be followed and will be censored for PFS and OS at week 16. DOR is defined as the time from first documentation of partial or complete response to first documented disease progression. Those patients who are currently on-study and progression-free at 16 weeks, will no longer be followed and will be censored for PFS and OS at week 16.

CONFIDENTIAL

This material is the property of the University of Pennsylvania. Do not disclose or use except as authorized in writing by the study sponsor.

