OS is defined as days from initiation of study therapy to death due to any cause or last subject contact. Those patients who are currently on-study and progression-free at 16 weeks, will no longer be followed and will be censored for PFS and OS at week 16.

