### ***8.2 Statistical Analysis Plan***

Based on evaluable subjects, the objective response rate and 95% confidence interval will be calculated. Duration of remission, progression-free survival and overall survival will be estimated by the method of Kaplan and Meier. Median values and 95% confidence intervals will be calculated. All observed toxicities will be graded and tabled. Toxicity tables will be separately constructed for cycles with pembrolizumab alone (cycles 1-2 and cycle  $\geq 5$ ) or pembrolizumab and itacitinib (cycles 3-4). Changes in immune pharmacodynamic biomarkers will be examined with scatter plots and summary statistics. Fold changes from baseline values will be estimated and summarized. **Sample Size:** The required sample size ranges from 11 to 48 evaluable subjects. In the event that 5% of subjects are not evaluable for objective response evaluation, the maximum sample size is 50 subjects. **Study Duration:** With an estimated accrual of 2 patients per month, it is anticipated that accrual will continue for approximately 24 months and subject follow-up will continue for up to year post Cycle 1/Day 1 (initiation of study treatment) for a total study duration of up to 36 months.

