##### **Overall Survival**

Overall Survival (OS) is defined as the time from initiation of study therapy to death due to any cause or last subject contact. Subjects without documented death at the time of the final analysis will be censored at the date of the last follow-up. Those patients who are currently on-study and progression-free at 16 weeks, will no longer be followed and will be censored for OS at week 16.

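### Median PFS, DOR and OS are planned although follow-up is limited to week 16 and scheduled scans end at week 12, and the OS cut-off is stated inconsistently

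*Combined protocol and SAP*

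**What the plan says.** **Planned summaries.** Section 8.2.3 (Secondary Objectives) estimates DOR, PFS and OS by Kaplan-Meier and adds: "Median values and 95% confidence intervals will be calculated". Section 8.2 says the same. Section 3.2 makes the median an objective for two of them: "To determine the median progression free survival (PFS) and duration of response (DOR) at week 12".

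**Horizon.** Section 2.1 describes the secondary endpoints as "progression free survival, duration of response and overall survival, up to week 16 when the subject reaches end of study". Section 3.2 also limits OS to week 16. Neither restricts this to particular subjects. The flow chart in 6.1 ends with the End of Study Visit at week 16 (±10 days).

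**Imaging.** Section 7.1.2.6 and the flow chart footnotes schedule a scan at about week 6, for biopsy planning, and one at week 12 for the primary outcome. Later imaging is optional and serves to confirm progression seen at week 12.

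**Censoring.** Section 4.2.3.1.2 says that subjects on study and progression-free at 16 weeks "will no longer be followed and will be censored for PFS and OS at week 16". The OS definition in 8.2.1 has the same restriction: subjects "progression-free at 16 weeks, will no longer be followed and will be censored for OS at week 16". Its general sentence censors everyone else still alive at last follow-up. For DOR, 4.2.3.1.2 says "DOR is defined as the time from first documentation of partial or complete response to first documented disease progression" and then names only PFS and OS as censored, whereas the DOR definition in 8.2.1 censors DOR at week 16.

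**Text pointing to longer follow-up.** Section 8.2 says "subject follow-up will continue for up to year post Cycle 1/Day 1 (initiation of study treatment", and closes that sentence "for a total study duration of up to 36 months". The Trial Summary (1.0) gives about 48 months. Section 10.2 mentions a survival follow-up phase that no schedule contains. Section 4.2.2 describes pembrolizumab as open-ended, while 2.1 and 5.3.2 give up to four cycles with an optional fifth.

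**The concern.** A median needs at least half the subjects to have had an event. Sixteen weeks is short for OS in a first-line setting. A response first read at week 12 leaves about four weeks and no scheduled scan before the end of study. Two of the three medians would then usually come out as not reached, with no other summary pre-specified. The objective of DOR at week 12 has the same difficulty, since a response first read at that scan has zero days of duration.

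The OS wording raises a separate question. If only progression-free subjects leave the risk set at week 16 and progressed subjects are followed further, the Kaplan-Meier curve after week 16 describes the group with the worse prognosis, and a median read from it would be too low.

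**Working it through.** The documents give no expected PFS, DOR or OS, so every event rate below is assumed. A median is taken as reached when at least half the subjects have an event, with no censoring before the horizon.

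**1. The plan's own figures.** The three-stage response-rate design reproduces by exact enumeration: false positive rate 0.0997 (stated 0.100), power 0.9057 (0.906), early termination 0.7857 (0.786). None of these depends on the present point. Study duration: 48 subjects at 2 per month is 24 months, and 24 + 12 = 36, so the 36-month total rests on the year of follow-up. With week 16 (112 days, 3.7 months) it would be 24 + 3.7 = 27.7 months.

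**2. Median OS, all subjects stopped at week 16.** P(Binomial(n, 1 − S) ≥ n/2), where S is survival at week 16:

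| n | S = 0.80 | S = 0.75 | S = 0.70 |
|---|---|---|---|
| 48 (maximum evaluable) | 3.3 × 10⁻⁶ | 0.0002 | 0.003 |
| 11 (stop after stage 1; 6 deaths needed) | 0.012 | 0.034 | 0.078 |

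OS uses the All Patients as Treated set, at most 50 subjects; at n = 50 and S = 0.70 the figure is 0.002.

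**3. Median DOR.** Take 21 responders, the smallest number that passes the final stage, and exponential durations. The event probability in a window of d days is q = 1 − 0.5^(d / median), and P(Binomial(21, q) ≥ 11) is:

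| Response first read | Window | True median 2 months | 3 months | 6 months |
|---|---|---|---|---|
| Week 12 | 28 days, every event found at once | 0.013 | 0.0007 | 1.5 × 10⁻⁶ |
| Week 6 | 42 days, progression found up to the week-12 scan | 0.13 | 0.013 | 0.0001 |

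The text does not say whether a response on the week-6 scan counts as first documented. The 42 days uses the day-42 scan of 7.1.2.6. Flow chart footnote 10 can be read as a different day, which would shift the second row.

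**4. Median PFS.** If 55% of evaluable subjects are responders at week 12, at most 45% can have progressed by then, so the median is not reached at the last scheduled scan. In general, with 48 subjects, P(median reached by week 16) is 0.80, 0.56, 0.29, 0.10 and 0.003 when 45%, 50%, 55%, 60% and 70% are truly progression-free at week 16.

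**5. Week-16 PFS.** With no scheduled scan after week 12, the week-16 value largely carries week-12 status forward. For exponential medians of 4, 6 and 9 months, true PFS at day 84 is 0.620, 0.727 and 0.809, and at day 112 it is 0.529, 0.654 and 0.753. The overstatement is at most 9, 7 and 6 points, and less where progression is found clinically.

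**6. OS if progressed subjects alone are followed past week 16.** Let L = 3.68 months, s = proportion alive at week 16, f = share of those who are progression-free, and mp and mq = median further survival of progression-free and progressed subjects.
- True curve: S(L + t) = s[f·0.5^(t/mp) + (1 − f)·0.5^(t/mq)].
- Kaplan-Meier curve under the restricted censoring: s·0.5^(t/mq).
- Example with s = 0.90, f = 0.60, mp = 24, mq = 6: the Kaplan-Meier median is 3.68 + 6·log₂(1.8) = 8.8 months, against a true 14.4 months, which is 39% low.
- Over s 0.80–0.90, f 0.5–0.7, mp 18–30 and mq 6–9 months, the median is 19% to 52% low.
- If everyone stops at week 16, this bias is zero.

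**The case against.** A median that is not reached is a legitimate Kaplan-Meier result. If all subjects stop at week 16, nothing false is printed for OS or DOR. Median PFS is more likely than not to be reached when half or fewer of the subjects are progression-free. This stands: the planned medians are poorly matched to the follow-up, but they are not invalid.

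A reader might infer that week-16 censoring of OS applies to progression-free subjects only, and hence that a biased OS median is to be expected. The documents do not support that. Sections 2.1 and 3.2 limit OS to week 16 without restriction, 5.7 and 7.1.6.1 bring subjects who discontinue treatment to an End of Study Visit, and no visit is scheduled later. The support for longer follow-up is the year in 8.2 and one phrase in 10.2, plus subjects treated past week 16 before Amendment V5, whose number is not given. The 19–52% is therefore conditional.

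A reader might also think that counting week-6 responses makes median DOR readily attainable. A full 70-day window to week 16 would give 0.68 at a true median of 2 months, but only if progression is detected after the last scheduled scan.

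Finally, 48 is the maximum evaluable number. Smaller trials give higher probabilities, as the 11-subject row shows.

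**Conclusion.** The concern holds in limited form. With follow-up ending at week 16, median OS is very unlikely to be reached. Median DOR is unlikely under the windows examined. Median PFS is unlikely if the regimen performs as hypothesised, but can be reached if it does not. These statements rest on assumed event rates, and for DOR on exponential durations.

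Separately, the documents contradict themselves on who is followed for OS and for how long. Stopping everyone at week 16 brings no bias but almost certainly no median. Following progressed subjects further could yield a median that is materially too low. The text does not settle which applies, though the visit schedule favours the former.

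The endpoints are secondary and descriptive, so the importance is minor to moderate. The text should be corrected. The response-rate test and the stopping rules are unaffected.

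**What to change.** 1. **OS cut-off.** Rewrite the OS censoring sentences in 4.2.3.1.2 and 8.2.1 so that one cut-off, week 16 as in 2.1 and 3.2, applies to all subjects regardless of progression, including those treated past week 16 before Amendment V5. List later OS data only.
2. **Summaries.** In 3.2, 8.2 and 8.2.3, plan the Kaplan-Meier PFS proportion at the week-12 assessment and the OS proportion at week 16, each with a 95% confidence interval. Report a median only if reached. Do not present week-16 PFS as scan-based.
3. **DOR.** Report the number of week-12 responders with no progression recorded by the End of Study Visit, noting that no scan is scheduled after week 12. Align 3.2, 4.2.3.1.2 and 8.2.1.
4. **Follow-up text.** Reconcile with the week-16 end of study the year of follow-up and 36-month total in 8.2, the 48 months in 1.0 and the survival follow-up phase in 10.2. The treatment-duration passages in 4.2.2, 2.1 and 5.3.2 also contradict each other and must be reconciled; which is right is not a statistical question.

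The cost is wording in the objectives, the definitions and the analysis plan. Sample size, the primary test and the PFS censoring rule do not change. The downside is that OS data after week 16 are listed rather than summarised.
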